3.2 Determination of Sample Size

A sample size of 25 evaluable subjects in each of the 3 treatment groups will have an 80% power to detect a 43% reduction in sPCR from Baseline to Week 24 between the pooled fostamatinib and placebo groups, using a 2-sided t-test with $\alpha = 0.05$ and log-transformed data. This calculation assumes that the 3 treatment groups have the same mean and standard deviations of urinary protein/creatinine ratio and coefficient of variation of 0.923 at Baseline and that the values for the placebo group remain constant over 24 weeks. Treatment allocation ratio will be 1:2 for the placebo: combined fostamatinib groups

Table 1 Study Treatment

Treatment Group	Number of Subjects	Dose
C	25	Placebo bid
A	25	Fostamatinib 100 mg bid
B	25	Fostamatinib 150 mg bid

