5.3 Biopsy Population

The biopsy population will include all randomized subjects who receive at least 1 dose of allocated study drug and have both baseline and end of studies biopsies from at least 8 glomeruli. The biopsy population will be used for all biopsy analyses.

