5.6 Adjustments for Covariates

The randomization stratification factors and the baseline values of the response variables will be included in the statistical analysis model as covariates.

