R_i = total number of tablets returned for visit interval i

$T_i = 2$ for bid dosing and $=1$ for qd dosing, for visit interval i

P_i = total number of days in visit interval i .

The total number of tablets that were supposed to be taken during the double-blind treatment period excludes the number of tablets not taken due to a dose interruption. If a patient fails to return a study drug kit dispensed during the double-blind treatment period, then study drug compliance is considered to be missing.

Baseline sPCR: Two baseline sPCR value will be used in the analysis. In primary efficacy analysis, the baseline sPCR is defined as the average of non-missing value between Visit 2 and the most recent screening value prior to Visit 2. If only one non-missing sPCR is available, this value will be used as baseline.

A **Treatment-Emergent Adverse Event (TEAE)** is any adverse event that emerges on or after first dosing and prior to the end of follow-up (having been absent prior to treatment) or worsens relative to the pre-treatment state.

Hy's Law criteria are: concurrent aspartate aminotransferase (AST) or alanine aminotransferase (ALT) $\geq 3x$ upper limit of normal (ULN) with total (and/or direct/conjugated) bilirubin (TBL) $> 2x$ ULN and alkaline phosphatase (ALP) $< 2x$ ULN, and no other reason can be found to explain the combination of increased aminotransferase and serum total bilirubin, such as viral hepatitis, alcohol abuse, ischemia, preexisting liver disease, or another drug capable of causing the observed injury.

Prior Medications will be defined as the medications used prior to the first dose of study drug. If the medication is used both prior to and on/after the first dose of study drug, the medication is both prior medication and concomitant medication.

Concomitant Medication will be defined as the medications used on/after the first dose of study drug.

7. Statistical Methods

The statistical analysis of the data obtained from this study will be performed using SAS® version 9.4 or higher. All inferential tests will be 2-sided and will be performed using a type I error rate of 5%, unless otherwise indicated.

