7.5 Analysis of Secondary Efficacy Endpoints

All secondary efficacy endpoints will be analyzed using the ITT population except for biopsy endpoints that will be analyzed using the Biopsy Population.

Continuous secondary endpoints will be analyzed using an ANCOVA model which includes the treatment and presence/absence of endothelial hypercellularity at baseline as factors and adjusted

for the baseline value. The LS mean differences between treatment groups (combined fostamatinib group vs placebo; 150 mg fostamatinib group vs placebo; 100 mg fostamatinib group vs placebo separately) accompanied by 95% confidence interval and the p-value for testing the treatment difference will be presented.

Shift tables will display the change in category from pre-study renal biopsy to post-treatment renal biopsy for each of the components of the Oxford Classification scoring:

- Mesangial hypercellularity (M_0 is $\leq 50\%$ of glomeruli show mesangial hypercellularity; M_1 is $> 50\%$ of glomeruli showing mesangial hypercellularity)
- Endocapillary hypocellularity (E_0 is no endocapillary hypercellularity; E_1 is any glomeruli showing endocapillary hypercellularity)
- Segmental glomerulosclerosis (S_0 = absent; S_1 present in any glomeruli)
- Tubular atrophy/interstitial fibrosis (T_0 is 0 – 25% of cortical area shows tubular atrophy or interstitial fibrosis; T_1 is 26 – 50%; T_2 is $> 50\%$)

Cochran–Mantel–Haenszel (CMH) test will assess whether there is an association between the change in these categories from pre-treatment to post-treatment and treatment group (combined fostamatinib group vs placebo; 150 mg fostamatinib group vs placebo; 100 mg fostamatinib group vs placebo separately) while controlling for the presence/absence of endothelial hypercellularity at baseline.

Missing data for the secondary endpoints will not be imputed.

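### The CMH tests of change in Oxford category ignore the component's own starting category, which usually costs power for S and T, less for M, and lets a baseline imbalance pass as change

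*SAP*

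**What the plan says.** SAP 7.5 plans shift tables for M, E, S and T from pre-study to post-treatment biopsy. A CMH "test will assess whether there is an association between the change in these categories from pre-treatment to post-treatment and treatment group", for pooled fostamatinib and for each dose against placebo, "while controlling for the presence/absence of endothelial hypercellularity at baseline". It names neither the CMH statistic (mean score or general association) nor how change is coded.

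Two other statements set a different standard. SAP 5.6: "The randomization stratification factors and the baseline values of the response variables will be included in the statistical analysis model as covariates". And the ANCOVA for continuous secondary endpoints, also in SAP 7.5, adjusts for the baseline value.

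The analysis set is the Biopsy Population of SAP 5.3: dosed subjects who "have both baseline and end of studies biopsies from at least 8 glomeruli". Missing secondary data are not imputed, and SAP 5.8 makes no multiplicity adjustment. SAP 4.3 lists category shifts as endpoints only for M and E; the tests for S and T appear only in 7.5. Protocol 10.3.2 planned Fisher's exact test for its categorical shifts, also without conditioning on the starting category.

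**The concern.** Change in a two- or three-level category is bounded by where it starts. An M0, S0 or T0 biopsy can only stay or worsen; an M1 or S1 biopsy can only stay or improve. A test stratified by E alone treats these subjects as interchangeable. Two things follow:

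- Variation in starting category enters the variance of the change score and hides real shifts.
- If the arms start with different mixes of S, T or M, the arm with more category-1 biopsies has more room to improve, and the test reads that as an effect on change.

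Randomisation is stratified only by E. The Biopsy Population is then a post-randomisation subset: Protocol 5.1 only encourages the end-of-treatment biopsy, and Protocol 7.2.2 does not require it after early withdrawal. The single-dose contrasts also use placebo pooled over two cohorts. Balance in starting S, T or M is therefore not assured in the set analysed. Histology is named in the efficacy objective.

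**Working it through.** **Inputs from the documents.** Two-sided 5% tests (opening of SAP 7). At most 50 fostamatinib v 25 placebo pairs (SAP 3.2: "Treatment allocation ratio will be 1:2 for the placebo: combined fostamatinib groups"). Strata: E only (SAP 7.5). Entry requires M1 and/or E1, and T0 or T1 (Protocol 6.1, criterion 4). **Not in the documents, so assumed:** switching rates, treatment effect on categories, number of biopsy pairs, CMH statistic, coding.

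**The plan's own figure.** The only stated power is for the primary endpoint. With "coefficient of variation of 0.923 at Baseline", log SD = √ln(1 + 0.923²) = 0.785; effect = −ln(0.57) = 0.562; SE = 0.785·√(1/25 + 1/50) = 0.192; noncentrality = 2.92. The t-test on 73 df has 82.2% power, so 25 per group is reproduced, slightly conservatively. It says nothing about the shift tests.

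**Where the power goes.** Code change as −1/0/+1. Let p be the prevalence of category 1, a the improvement rate from it and b the worsening rate from category 0.

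- Variance within starting category: W = p·a(1−a) + (1−p)·b(1−b).
- Extra variance from mixing starting categories: B = p(1−p)(a+b)².
- The conditioned test faces W; the planned test faces W + B. If the conditioned test has 80% power, the planned one has about Φ(2.80·√r − 1.96), with r = W/(W+B).

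| p | a / b | W | B | r | Planned power |
|---|---|---|---|---|---|
| 0.5 | 0.1 / 0.1 | 0.090 | 0.010 | 0.90 | 75.7% |
| 0.5 | 0.2 / 0.2 | 0.160 | 0.040 | 0.80 | 70.7% |
| 0.5 | 0.4 / 0.3 | 0.225 | 0.1225 | 0.65 | 61.6% |

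This is a small-effect approximation. With a large effect the fostamatinib arm itself switches more, so simulated losses at a given placebo rate are larger.

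**Simulation (50 v 25, effect tuned to about 80% power for the conditioned test, component independent of E, prevalence 50% or 70%).** Points of power lost by the planned test:

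| Placebo switching each way | 1-df score | 2-df general association |
|---|---|---|
| 5-10% | 3-15 | 6-19 |
| 20% | 9-23 | 4-25 |
| 30-40% | 15-33 | 6-34 |
| M, entry rule imposed, 10-40% | 0-16 | 2-26 |

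Excluding the M row, 20 points or more occurred in 6 of 19 scenarios (score) and 5 of 19 (2-df). For M it was none and 3 of 24. At 30 v 15 the loss reached 37 points.

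Two fixed cases show the spread. With 40 v 20 pairs, prevalence 60%, improvement 70% v 30% and worsening 30% v 70% (fostamatinib v placebo), power is 56% as planned and 84% conditioned. With 50 v 25, placebo switching 10% each way and fostamatinib 40% improving and 5% worsening, it is about 39% v 46%.

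**Type I error.** Over randomisation the planned test rejects in 4.1-5.3% of null trials. Now fix a split of 60% v 40% in 50 v 25 (pooled p = 0.533), with no treatment effect and switching q each way. The expected difference in mean change is 0.2·2q.

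- q = 0.4: shift 0.16; rejection limit 1.96·√(0.399·0.06) = 0.303; conditional SE √(0.24·0.06) = 0.12. The rejection rate is 1 − Φ((0.303 − 0.16)/0.12) ≈ 12% (simulated 11%).
- q = 0.1: shift 0.04, limit 0.152, SE 0.0735. The rate is about 7% (simulated 6.5%).
- At an exact 50/50 split in both arms the planned test is conservative: 1.5-3.7% simulated.

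If 60% v 40% is instead the underlying prevalence in the subset, so that the realised gap varies around 20 points, the simulated rate is 7-17% for q from 0.1 to 0.4. The conditioned test stays at about 4-6% throughout. By chance alone, at 50% prevalence the SD of the gap is √(0.25·0.06) = 0.122, and a gap of 20 points or more has about a 12% probability.

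**E.** Here the stratum is the starting category, and the two tests gave identical p-values.

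**Limit.** Components were simulated as binary; a move to T2 was not modelled.

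**The case against.** The strongest reply has four parts.

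- **The large losses come from assumed inputs.** They need roughly 20-40% of placebo subjects to change category each way within 24 weeks, or very large effects. This stands: 20 points is reachable, not typical.
- **The test is valid over randomisation.** This also stands. A reader might infer that the planned test has an inflated error rate, or that it is really a test of baseline mix. The documents do not support that: with equal expected mix the size is about 5%, and the distortion arises only given an imbalance. Stratifying on observed category would not cure selection into the Biopsy Population in general either.
- **Under some codings the unconditioned test is no weaker.** With improvement-only effects, improved yes/no reached 84% against 80%, and a four-shift-cell test 75-96% against about 80%. This is true, but the SAP does not say which coding applies, and that is itself a gap.
- **The exposed tests are peripheral.** M is already partly conditioned, because an E0 subject must be M1 unless waived. S and T category shifts are not listed in SAP 4.3. The underlying histology scores are analysed by baseline-adjusted ANCOVA. A reader might infer that histology lacks any baseline-adjusted analysis; it does not.

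None of this explains why the rule in SAP 5.6 is applied to the ANCOVA and not to the CMH test.

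**Conclusion.** The point holds for S and T, and to a lesser degree for M; E is unaffected. The CMH sentence in SAP 7.5 does not carry through SAP 5.6. Power is usually lost, by about 0 to 35 points on assumed switching rates, effects and statistics. A flat claim of 20 or more points would be too strong, since the documents give no switching rates. Error control holds on average and weakens only when the arms happen to differ in starting category, whether by chance or through who provides a second biopsy. Because these are secondary tests without multiplicity control in a proof-of-concept study, the consequence is limited: a histologic shift may be missed or misread, but the primary result is untouched.

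**What to change.** In SAP 7.5, replace the CMH sentence with text to this effect: for each Oxford component, the post-treatment category (scored 0/1, or 0/1/2 for T) will be compared between treatment groups with a CMH row-mean-scores test, stratified by that component's pre-treatment category and by the randomisation stratum; for E, by pre-treatment E category alone; an exact p-value will be used where strata are sparse. Keep the shift tables.

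For E, also state which baseline reading is used. Protocol 5.1 has one panel member set the stratum and the full panel score the biopsy after randomisation, so the two may differ.

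The cost is one sentence and one more stratification variable, with no new data. The downside is up to four strata in at most 75 pairs, so thin strata contribute little. Where treatment mainly produces improvement, some other codings would do as well, and the gain there may be small or nil.

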4.3 Secondary Efficacy Endpoints

The following are the secondary efficacy endpoints considered for this study:

- Spot protein to creatinine ratio (sPCR):
 - Mean change from Baseline of sPCR at Week 12
 - Percentage of subjects with $\geq 30\%$ reduction in sPCR from Baseline at Week 24
 - Percentage of subjects with $\geq 50\%$ reduction in sPCR from Baseline at Week 24
 - Percentage of subjects with sPCR < 500 mg/g at Week 12
- Estimated glomerular filtration rate (eGFR):
 - Mean change from Baseline of eGFR (mL/min/1.73 m²) at Week 12
 - Mean change from Baseline of eGFR (mL/min/1.73 m²) at Week 24
- Haematuria (dipstick test):
 - Shift in haematuria (dipstick test) from baseline to Week 12
 - Shift in haematuria (dipstick test) from baseline to Week 24
- Biopsy Endpoints:
 - Mean change from pre-treatment to post-treatment in mesangial hypercellularity score (sum of mesangial scores/number of scoreable glomeruli) on renal biopsies
 - Shift in M Oxford Classification from pre-study renal biopsy to post-treatment renal biopsy
 - Mean change from pre-treatment to post-treatment in endocapillary hypercellularity score (sum of endocapillary scores/number of scoreable glomeruli) on renal biopsies
 - Shift in E Oxford Classification from pre-study renal biopsy to post-treatment renal biopsy

- Mean change from pre-treatment to post-treatment in cellular/fibrocellular crescent score (sum of cellular/fibrocellular crescent scores/number of scoreable glomeruli) on renal biopsies
- Mean change from pre-treatment to post-treatment in segmental sclerosis/adhesion score on renal biopsies (sum of segmental sclerosis/adhesion scores/number of scoreable glomeruli)
- Mean change from pre-treatment to post-treatment in global glomerulosclerosis score on renal biopsies (sum of global sclerosis scores/number of scoreable glomeruli)
- Mean change from pre-treatment to end of post-treatment in tubulointerstitial scarring on renal biopsies

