7.4.1 Main Analysis

The primary efficacy endpoint will be analyzed using an analysis of covariance (ANCOVA) model based on the ITT population. The ANCOVA model will include both the treatment groups and the presence/absence of endothelial hypercellularity at baseline as factors and adjust for the sPCR at baseline (as a covariate). If required and when possible, missing Week 24 data will be imputed using an appropriate Multiple Imputation (MI) procedure. Should Multiple Imputation procedures fail, last observation carried forward (LOCF) will be used as an alternative imputation algorithm.

The regression method for monotone missing data (SAS PROC MI) will be used for multiple imputation. For patients who discontinued the study due to adverse events, consider the missing data mechanism for the missing change from baseline values to be missing not at random (MNAR). For patients who discontinued the study due to reasons other than adverse events or patients who completed the study but have missing data at a visit, consider the missing data mechanism for the missing change from baseline values to be missing at random (MAR).

Missing data will be imputed in two separate subgroups. The first subgroup will contain all patients randomized to a Fostamatinib group that have data available at the visit or have a MAR missing data mechanism. The second subgroup will contain all patients randomized to placebo as well as fostamatinib patients missing data at the visit with an MNAR missing data mechanism.

Multiple imputation will then be performed within each subgroup, resulting in missing data for Fostamatinib patients under an MAR missing data mechanism imputed from a model obtained only from Fostamatinib treated patients, and missing data from all placebo patients as well as Fostamatinib treated patients with an MNAR missing data mechanism imputed from a model obtained only from placebo treated patients. After obtaining complete data sets for both subgroups, the complete data sets after combining subgroups will be used in the analysis, and inferences from each complete dataset will be combined to obtain an overall test statistic.

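### The Week 24 sPCR responder endpoints are left unimputed with no stated denominator, which is inconsistent with how the SAP treats the same missing value in the primary analysis

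*SAP*

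**What the plan says.** **Primary endpoint.** SAP 7.4.1 states that "missing Week 24 data will be imputed using an appropriate Multiple Imputation (MI) procedure". Discontinuation for an adverse event (AE) is treated as missing not at random. Fostamatinib subjects who leave for that reason are imputed from a placebo model; those who leave for other reasons are imputed from fostamatinib subjects. SAP Appendix E creates ten imputed datasets.

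**Responder endpoints.** SAP 4.3 lists two secondary endpoints, the percentages of subjects with a ≥30% and a ≥50% "reduction in sPCR from Baseline at Week 24". SAP 7.5 then says "Missing data for the secondary endpoints will not be imputed". SAP 11.1 and protocol 10.8 give the same rule.

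**Population and test.** SAP 5.1 and 7.5 assign these endpoints to the ITT population of all randomised subjects. Neither says how a subject without a Week 24 sPCR is classified. SAP 7.5 names no test for the sPCR responder percentages. Protocol 10.3.2 gives Fisher's exact test, pooled fostamatinib against placebo, for the ≥30% endpoint and does not list the ≥50% endpoint.

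**When Week 24 is empty.** Protocol 7.9 provides a withdrawal visit with the Week 24 assessments, including sPCR. SAP Section 10 assigns assessments by study day, and the Week 24 window is Day 148 to 180. A withdrawal sPCR before Day 148 therefore goes to an earlier visit.

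**The concern.** The primary analysis takes the position that AE dropout carries information about outcome and that a fostamatinib subject who leaves for an AE should not be credited with the drug's effect. The responder endpoints use the same measurement at the same visit but do not carry that position over. If missing values are neither imputed nor assigned a category, those subjects drop out of both numerator and denominator, and the rate is calculated among those who stayed.

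The gap covers anyone who withdraws before Day 148 for any reason. AE dropouts matter most because the SAP itself calls them informative. Protocol 3.5 describes dose-dependent effects on blood pressure, neutrophils, the gut and liver tests, so higher dropout on fostamatinib is plausible, though the documents do not quantify it. If it happens, and dropouts respond less often than completers, the responder difference will look better than the primary result from the same data. The missing denominator also leaves a choice that could be made after the data are seen.

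**Working it through.** **1. The plan's own figure.** SAP 3.2 says that "25 evaluable subjects in each of the 3 treatment groups will have an 80% power to detect a 43% reduction in sPCR", with "coefficient of variation of 0.923 at Baseline", "values for the placebo group remain constant over 24 weeks" and "Treatment allocation ratio will be 1:2 for the placebo: combined fostamatinib groups"; alpha is two-sided 5%.
- Log-scale SD = √ln(1 + 0.923²) = 0.785; effect = −ln(1 − 0.43) = 0.562.
- Standard error with 25 placebo and 50 fostamatinib = 0.785 × √(1/25 + 1/50) = 0.192.
- Power is 83.2% by the normal approximation and 82.2% by the noncentral t. The t-test first reaches 80% at 24 + 48 subjects (80.6%).

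The stated sample size therefore reproduces. It is expressed in evaluable subjects, and neither document gives a dropout rate.

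**2. Simple illustration (all rates assumed).** Observed-case response 45% vs 25%, difference 20 points; missing Week 24 values 20% on fostamatinib and 8% on placebo.
- Missing counted as non-response: 0.45 × 0.80 − 0.25 × 0.92 = 0.36 − 0.23 = **13 points**.
- All fostamatinib dropouts at the placebo rate: 0.45 × 0.80 + 0.25 × 0.20 − 0.25 = **16 points**.
- Half of them AE dropouts at the placebo rate, the rest at the fostamatinib rate: 0.45 × 0.90 + 0.25 × 0.10 − 0.25 = **18 points**.

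The third line is closest to SAP 7.4.1, which uses the placebo model only for AE discontinuations. With 10% vs 4% missing, the first two figures become 16.5 and 18 points.

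**3. Illustration from the plan's inputs.** Assume that the log SD of 0.785 applies to the log change and that placebo is unchanged.
- ≥30% response: placebo Φ(ln 0.70 / 0.785) = 32.5%; fostamatinib Φ((ln 0.70 + 0.562) / 0.785) = 60.3%.
- ≥50% response: 18.9% and 43.4% by the same formulas with ln 0.50.

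Let a fraction of fostamatinib subjects be missing, all through AEs, and no placebo subjects. Differences in percentage points:

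| Endpoint | Handling | 10% | 20% | 30% |
|---|---|---|---|---|
| ≥30% | observed cases | 27.8 | 27.8 | 27.8 |
| ≥30% | placebo rate | 25.1 | 22.3 | 19.5 |
| ≥30% | non-response | 21.8 | 15.8 | 9.7 |
| ≥50% | observed cases | 24.5 | 24.5 | 24.5 |
| ≥50% | placebo rate | 22.1 | 19.6 | 17.2 |
| ≥50% | non-response | 20.2 | 15.8 | 11.5 |

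At 20% dropout the observed-case difference for ≥30% response exceeds the placebo-rate version by 0.20 × 27.8 ≈ 5.6 points and the non-response version by 0.20 × 60.3 ≈ 12 points.

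**4. Worst case under no drug effect.** If every AE dropout would have been a non-responder and no placebo subject is missing, the observed fostamatinib rate is the placebo rate divided by (1 − dropout). The two-sided Fisher rejection rate for ≥30% response rises from 3.6% with complete data to 4.5%, 8.0% and 15.5% at 10%, 20% and 30% dropout. For ≥50% response it rises from 3.3% to 3.5%, 4.9% and 7.2%.

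The placebo-rate figures simplify the planned imputation, which also conditions on baseline and earlier visits.

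**The case against.** The strongest reply is that the endpoints are percentages of subjects in an ITT population of everyone randomised. Keeping all randomised subjects in the denominator is then a fair reading, and it would not favour the drug if fostamatinib dropout is higher. This has force: removal of dropouts is an inference, not something the SAP states. But counting a missing value as non-response is itself an imputation, and the SAP says there will be none. In SAP Section 8, for the interim analysis, the absence of imputation goes together with reporting observed data only. Either way the denominator has to be written down.

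The rule is also deliberate and identical in both documents. Dropout is already handled for the endpoint that carries the conclusion, with an LOCF sensitivity analysis. Both facts stand and limit the consequence, but neither reconciles the responder rule with SAP 7.4.1.

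A reader might go further and infer that the plan excludes AE dropouts and so biases the responder results toward fostamatinib. The documents do not support that as fact:
- They give no dropout rates.
- Protocol 3.5 calls the known effects reversible and manageable, and protocol 7.4 provides stepwise dose reduction before discontinuation, so toxicity need not mean a missing Week 24 value.
- A withdrawal sPCR within Day 148 to 180 counts as Week 24.
- Even in the worst case above, rejection at 10% dropout stays below 5% for both endpoints.

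Nor is this a conflict between protocol and SAP.

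**Conclusion.** The inconsistency is real and worth correcting. The Week 24 responder endpoints have no imputation and no stated denominator, and are most naturally read as observed-case analyses. The same missing sPCR is treated as informative in the primary analysis when a fostamatinib subject leaves for an AE.

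Under the assumed 45% vs 25% response and 20% vs 8% missing, a 20-point observed-case difference falls to about 18 points when half of the fostamatinib dropouts take the placebo rate, 16 when all do, and 13 when missing counts as non-response. All these rates are assumptions. The direction depends on dropout being higher on fostamatinib and on dropouts responding less often than completers.

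The effect is on the interpretation of secondary endpoints, which carry no multiplicity adjustment, in a phase 2 proof-of-concept study. It does not touch the primary conclusion.

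**What to change.** 1. Derive the ≥30% and ≥50% Week 24 indicators in each imputed dataset of SAP 7.4.1. Use the responder endpoints' own baseline, the last pre-dose (Visit 2) value, and not the average of screening and Visit 2 used in the main primary analysis. If the imputed variable is the change from the averaged baseline, recover the Week 24 sPCR first.
2. Analyse each dataset with a method that gives an estimate and standard error, for example a risk difference or a logistic regression adjusted for the endocapillary stratum, and combine by Rubin's rules. This replaces Fisher's exact test for this analysis, because that test does not supply the estimate and standard error that the usual combining rules need. It also gives the ≥50% endpoint a named method.
3. Report missing = non-responder, with all randomised subjects in the denominator, as a sensitivity analysis, and observed cases as supportive with the number analysed per arm.
4. Align SAP 7.5, SAP 11.1 and protocol 10.8 with this rule.

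The cost is revised wording, a little extra programming to merge in the second baseline, and a change of test for the responder endpoints. No new data are needed, and the imputed datasets are already planned.
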